### **1.5.2 Risk with Radiation Therapy (RT)**

Salvage re-irradiation has long been offered as a treatment modality for recurrent GBM patients and has been established to be generally safe and well tolerated (see Section 1.1.4). However, the risk of radiation necrosis and other adverse events listed below are increased in the setting of re-irradiation for glioma.

Expected acute radiation therapy adverse events include skin reaction, including dryness, redness, itching (pruritis), tanning, soreness and hair loss, fatigue, nausea, vomiting, dry mouth, altered taste, decrease in blood counts, short-term hearing impairment due to reactions in the ear canals and on the ear, serous otitis media (fluid in the middle ear) as well as temporary aggravation of brain tumor symptoms such as headaches, seizures, and weakness.

Expected early delayed radiation therapy adverse events (occurring 1-3 months after radiotherapy treatment) include fatigue, lethargy and transient worsening of existing neurological deficits.

CONFIDENTIAL

Expected late delayed radiation therapy adverse events (occurring 3 months or more after radiation therapy treatment) include radiation necrosis (severe local damage to normal brain tissue), which may result in permanent neurocognitive deficits (difficulties with short term memory, calculations, language and more severe neurocognitive deficits) or motor dysfunction, leukoencephalopathy, permanent hearing impairment, radiation injury to the visual structures including the optic nerve and chiasm, which can result in partial or complete blindness, cataracts endocrine dysfunction and radiation-induced neoplasms. Radiation necrosis can mimic recurrent brain tumor and may require surgery for diagnosis and treatment.

To minimize risk to the subject, modern RT techniques will be used including fractionated stereotactic radiotherapy, protons, and IMRT, which allow for highly conformal treatment to a considerably more precise target volume. These technologies have the potential to significantly reduce the toxicity associated with re-irradiation. Fractionated and hypofractionated RT (HFRT) have well-established safety and adverse event profiles and is generally well tolerated in recurrent GBM patients, with uncommon occurrences of late CNS toxicity and radiation necrosis (see **Section 1.1.4**).

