### 3.4 Primary Safety Endpoints

For the overall endpoints of the Safety Lead-In portion of the study, see **Section 3.2.1**. Safety summaries will be reported for both the Safety Lead-in and the phase II trial. All subjects who received at least one dose of Avelumab and/or radiation will be used for the analysis of safety data in this study. Safety and tolerability will be assessed by clinical review of all relevant parameters including adverse experiences (AEs), laboratory tests, and vital signs.

For the phase II portion of the study, we consider a rate of toxicity of 40% or greater (defined as CTCAE grade 3, grade 4, or intolerable grade 2 toxicity that is possibly, probably, or definitely related to study therapy) to be unacceptable. We will conduct an interim assessment for safety after 10 patients are treated for at least 2 cycles (56 days) and again after 18 patients are treated for at least 2 cycles (56 days). If there are 7 or fewer unacceptable toxicities among the first 10 patients, the trial will continue and not be stopped for safety. After safety analysis of 18 patients, the trial will continue if there are 11 or fewer patients with an unacceptable toxicity. These analyses are not adjusted for multiple assessments and at each analysis, there is a 5% alpha level and 80% power. At the conclusion of the trial, with 43 patients, the trial would be considered to have an unacceptably high toxicity rate if 24 or more patients experienced the specified toxicities.

Due to a possible increased incidence of CNS toxicity from delayed radiation necrosis or radiation injury occurring during the first 6 months post RT, a special interim analysis will be performed. After the first 20 subjects treated at the RP2D, including subjects in the Safety Lead-In portion of the trial, have a minimum 24 week overall survival follow-up time from the end of RT, an interim safety analysis for delayed treatment-induced neurotoxicity will be performed. If the incidence of CTCAE grade  $\geq 3$  CNS (neurologic) toxicity deemed possibly, probably, or definitely related to treatment is 30% or higher in this group, the trial will be halted due to lack of safety.

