## 6.8 Post Treatment Procedures

**Follow up post-treatment:** All participants will be followed until resolution or stabilization of any serious or reportable adverse events occurring during treatment or starting within 30 days of last study drug. After the end of treatment, each subject will be followed for 30 days for adverse event monitoring and 90 days for serious adverse event reporting. Assessments may continue for ongoing reportable adverse events. Participants removed from protocol therapy for unacceptable adverse events will be following until resolution or stabilization of the adverse event.

**30-day post-drug visit:** A site visit is to be performed at 30 days ( $\pm 7$  days) after the last study drug is given, unless the subject is unable to travel due to deteriorating medical condition, due to the potential risk for delayed immune-related toxicities. The visit will include the safety procedures detailed below:

- Adverse event assessment.
- Symptom-directed physical exam and KPS assessment.
- Vital signs: weight, temperature, resting blood pressure, pulse and respiration rate.

CONFIDENTIAL

- Serum chemistry: sodium, potassium, chloride, bicarbonate, calcium, magnesium, phosphorous, glucose, albumin, creatinine, blood urea nitrogen (BUN), uric acid, ALT, AST, total bilirubin, direct and/or indirect bilirubin, alkaline phosphatase (ALP), and lactate dehydrogenase (LDH).
- Hematology: WBC count, 3-cell differential (ANC, monocyte count, lymphocyte count), hemoglobin, hematocrit, and platelet count.

**90-day post-drug safety follow-up:** An extended safety follow-up is to be performed at 90 days ( $\pm 14$  days) after the last study drug is given. This may be performed via documented phone conversation with a study nurse or clinician or physician.

**Extended follow-up post-treatment:** Subjects should be contacted every 3 months ( $\pm 14$  days) for survival status and initiation of any new anti-cancer treatments until death, withdrawal of permission to record at least survival data, or subject is lost to follow-up. Contact may include clinic visit, telephone contact, e-mail, mail or medical record review. The date of death, initiation of any new anti-cancer treatments and date of last contact should be documented.

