### **Adverse Event Reporting Period**

The study period during which adverse events must be reported is normally defined as the period from the initiation of any study procedures to the end of the study treatment follow-up. For this study, the study treatment follow-up is defined as 30 days following the last administration of study treatment.

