### 8.2.2 Evaluation of Causality

#### Relationship of AEs to Study Drug:

The relationship of AEs to study drug will be assessed by the investigator, and will be a clinical decision based on all available information. The following question will be addressed:

Is there a reasonable possibility that the AE may have been caused by the study drug?

The possible answers are:

**Not Related:** There is no reasonable possibility that the event may have been caused by the study drug

**Related:** There is a reasonable possibility that the event may have been caused by the study drug.

The sponsor will request information to justify the causality assessment of SAEs, as needed.

**Attachment 5** lists factors to consider in assessing the relationship of AEs to Avelumab or infusion procedures, radiation therapy, combination treatment, study procedures, or background treatment.

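### The delayed CNS-toxicity halting rule may undercount events in subjects who stop treatment early, because its 24-week condition is survival follow-up while scheduled AE and SAE collection ends 30 and 90 days after the last dose

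*Combined protocol and SAP*

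**What the plan says.** Section 3.4 adds a special interim analysis because CNS injury from radiation may appear late, "occurring during the first 6 months post RT". It is run when the first 20 subjects treated at the RP2D, including those from the Safety Lead-In, "have a minimum 24 week overall survival follow-up time from the end of RT". The trial is halted if the incidence of grade 3 or higher CNS "toxicity deemed possibly, probably, or definitely related to treatment is 30% or higher in this group". Section 1.5.2 gives the expected timing of the main hazard: "Expected late delayed radiation therapy adverse events (occurring 3 months or more after radiation therapy treatment) include radiation necrosis".

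The collection windows run from the last dose, not from RT. Under Section 6.8, with the same windows in 3.1.2 and 4.5.2, "each subject will be followed for 30 days for adverse event monitoring and 90 days for serious adverse event reporting". Section 8.1 sets a single, shorter reporting period: "the study treatment follow-up is defined as 30 days following the last administration of study treatment". After that, the 3-monthly contacts in 6.8 are "for survival status and initiation of any new anti-cancer treatments until death". Toxicity is not listed there, and record review is enough to count as a contact. For causality, Section 8.2.2 asks "Is there a reasonable possibility that the AE may have been caused by the study drug", answered as related or not related.

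**The concern.** The analysis point is defined by how long subjects have been followed for survival. The numerator depends on how long they have been followed for toxicity. These are different clocks. A subject who stops early can complete 24 weeks of survival follow-up with no scheduled question about neurologic toxicity for much of that time, and still enter the denominator of 20 as event-free.

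The error runs one way. A missed event can only lower the observed rate and favour continuing. This is the one rule in the plan dedicated to delayed neurotoxicity, the overlapping hazard that Section 1.5.3 identifies, and the least covered part of the period is the part in which Section 1.5.2 expects necrosis.

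**Working it through.** Section 3.4 states no error rate or power for this rule, so there is no planned figure to reproduce.

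**Calendar.** HFRT runs Day 8 to Day 12 (5.2.2). End of window: 12 + 24 × 7 = Day 180.
- AE monitoring reaches Day 180 only if the last dose is on or after 180 − 30 = Day 150.
- SAE reporting reaches it only if the last dose is on or after 180 − 90 = Day 90.

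**One subject, no modelling.** A subject who stops at the first scheduled scan, before C3D1, had the last dose at C2D15, which is Day 43. AE monitoring ends at Day 73 and SAE reporting at Day 133, 47 days short of Day 180. Three months after RT is about Day 102, so AE monitoring has ended before that period begins. By contrast, a subject whose last dose is at 4 months (about Day 122) has AE cover to Day 152, 28 days short, and SAE cover to Day 212, which is enough.

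**Subjects affected.** The documents give no distribution for the time of last dose. I assume it is exponential, S(t). The 4-month median (121.75 days) is the expected participation in 3.1.2. As an alternative, S is scaled to PFS6 of 0.60 at 168 days (7.1.3, 7.2.2).
- Last dose before Day 150: 1 − S(150) = 57% (4-month median) or 37% (PFS6 0.60), about 11 or 7 of 20.
- Last dose before Day 90: 1 − S(90) = 40% or 24%, about 8 or 5 of 20.

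**Share of events outside scheduled cover.** Assume events spread evenly over Days 12 to 180 (168 days). With window w, T = 180 − w and λ = ln 2 / 121.75 = 0.00569:

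U = [T − (1 − S(T))/λ] / 168

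- w = 30: T = 150, S = 0.426, U = (150 − 100.9)/168 = 0.292.
- w = 90: T = 90, S = 0.599, U = (90 − 70.4)/168 = 0.117.
- At PFS6 0.60 the same formula gives 0.176 and 0.067.

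**Chance of halting.** 30% of 20 is 6, so P(halt) = P(X ≥ 6), with X binomial (20, p(1 − U)). All events outside scheduled cover are taken as missed.

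| True rate p | Full capture | AE window, U = 0.292 | SAE window, U = 0.117 |
|---|---|---|---|
| 0.30 | 0.584 | 0.238 | 0.444 |
| 0.40 | 0.874 | 0.517 | 0.764 |
| 0.50 | 0.979 | 0.766 | 0.936 |

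At p = 0.40 the effective rates are 0.40 × 0.708 = 0.283 and 0.40 × 0.883 = 0.353. With the PFS6 0.60 shares, P(halt) at p = 0.40 is 0.69 and 0.82.

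**The case against.** The strongest reply is that the rule counts only related events, and late related events stay reportable. Sections 8.1 (post-study events), 8.3, 8.4 and 8.4.1 call for reporting of late SAEs, and in most of these places other AEs of concern, that the investigator considers related, with no end date. Grade 3 or higher symptoms suspected to come from brain edema are AESIs, reportable within 24 hours of awareness. Under 5.2.3.7, subjects who stop Avelumab without withdrawing are asked to attend remaining visits, or continue in the follow-up phase, until progression or study closure. Those removed for unacceptable AEs are followed until the event settles. Many grade 3 or higher neurologic events would be serious, so the 90-day window often applies.

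Most of this stands, and it limits the claim to active ascertainment in early stoppers. It does not close the gap. Reporting under 8.4.1 begins when the investigator is informed, and nothing schedules the question. The 5.2.3.7 visits end at progression, and Section 1.5.2 warns that necrosis can mimic recurrence, so a necrosis case called progression leaves those visits.

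Four stronger readings are tempting, and the documents do not support them:
- *The rule does undercount, by a known amount.* The late-reporting duties make this a possibility, and the documents give no missed fraction.
- *About 46% (AE window) or 25% (SAE window) of all events are missed.* Those shares apply only to Days 102 to 180 under the same model. The rule covers the whole period after RT, and Section 1.5.2 also lists acute and early-delayed neurologic effects.
- *Early deaths are excluded.* The trigger wording can be read that way, but 3.4 also defines the group as the first 20 treated and puts every treated subject in the safety analysis. The text is unclear.
- *Radiation injury cannot be attributed.* The question in 8.2.2 names only the drug, but 8.4 states that study treatment includes radiation, and 8.2.2 refers to Attachment 5 for radiation and combination treatment.

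**Conclusion.** The concern holds as a risk of undercounting in subjects who stop early. The windows and the survival-based trigger are plain in the text, and Days 150 and 90 follow by calendar arithmetic alone. Subjects treated beyond those days are fully covered.

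The size is not known. The fall from 87% to about 52% or 76% at a true 40% rate rests on exponential time on treatment, a 4-month median taken from standard therapy, evenly spread events and no passive reporting. It also counts time after death as uncovered. With that event timing these are upper-side effects: passive reporting, the visits under 5.2.3.7 or longer treatment would shrink them. Events concentrated late in the window would enlarge them.

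The case for change does not depend on the model. As written, any loss biases a safety halt towards continuing, and the remedy is cheap.

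**What to change.** Amend 3.4, 6.8 and 8.1 as follows:
- For each of the first 20 subjects treated at the RP2D, actively ask about and record grade 3 or higher neurologic AEs, with onset dates, until 24 weeks after the end of RT or death, whether or not treatment has stopped. Use the 90-day and 3-monthly contacts already planned.
- Run the analysis when each of the 20 has been assessed for toxicity to 24 weeks after RT or has died. Keep all 20, including early deaths, in the denominator.
- State that relatedness for this rule means related to Avelumab or HFRT, on the scale that 3.4 uses, and align 8.2.2 with it.
- Reconcile the 30-day period in 8.1 and 8.4.1 with the 90-day SAE window in 3.1.2, 4.5.2 and 6.8.

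The cost is protocol wording and one added question at existing contacts, with no new visits. A 3-monthly contact may fall after Day 180, so the analysis waits for the first contact at or after 24 weeks or that contact is brought forward. Attribution will be less certain after progression or new therapy, but the events will at least be on record for review.

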## 4 Subject Selection and Withdrawal

### 4.1 Inclusion Criteria

1. Male or female subjects aged  $\geq 18$  years.
2. Documentation of *IDH1* or *IDH2* mutation in any tumor specimen.
3. Pathologic evidence (either diagnostic pathology slides or pathology report) of a diagnosis of WHO grade II or III glioma prior to treatment with temozolomide or PCV chemotherapy.
4. Histopathological evidence of glioblastoma (WHO grade IV) on a progressive tumor specimen after treatment with temozolomide or PCV chemotherapy. The diagnosis of glioblastoma must be confirmed on central review by a study-designated neuropathologist at NYULMC at screening. Exceptions to this eligibility include the following:
  - a. Any progressive glioma with *IDH1* or *IDH2* mutation, regardless of WHO grade, histopathological diagnosis, or prior therapy, will be eligible if the progressive tumor specimen is found to have one of the genetic alterations below:
    1.  $\geq 20$  somatic mutations per Mb by whole-exome sequencing
    2. High mutation burden or microsatellite instability (MSI) identified by Foundation Medicine panel next-generation sequencing (FoundationOne®, FoundationOne CDx™). Foundation Medicine's threshold for high mutation burden (HMB) in their panel NGS assays is  $\geq 20$  somatic mutations per Mb. Foundation Medicine's panel NGS assay has been validated by whole-exome and whole-genome sequencing to correlate tightly with tumor mutation burden ( $R^2 = 0.94$ ).
    3. Mutation in a mismatch repair gene or other genes known to be associated with hypermutator phenotypes or microsatellite instability, including but not limited to *MSH2*, *MSH6*, *MLH1*, *POLE*, *PMS2*, *POLD* as determined by validated methods.
    4. Microsatellite instability as identified by polymerase chain reaction (PCR) or other validated methods.
  - b. Progressive oligodendroglioma (with 1p/19q codeletion) that has hallmark histopathological features of glioblastoma (i.e. necrosis, pseudopalisading necrosis, or microvascular proliferation) is eligible as *IDH1/2* mutant, 1p/19q codeleted oligodendrogliomas that have progressed after chemotherapy have been shown to develop hypermutation phenotype.
5. Availability of a paraffin-embedded or frozen tumor-tissue block with a minimum of 1 cm^2 of tumor surface area from a tissue specimen that demonstrates pathological transformation to glioblastoma (WHO grade IV) or a progressive specimen that harbors one of the genetic alterations specified in Inclusion Criteria 4a.
  - a. If a tumor block cannot be submitted, then 20 unstained slides (preferably 10 slides from two different tumor blocks from the same surgery) from the tumor specimen must be submitted.
6. Patients must have had treatment with temozolomide, lomustine (CCNU) or PCV [procarbazine, lomustine (CCNU), vincristine] chemotherapy prior to histopathologic transformation to glioblastoma or prior to identification of one of the genetic alterations specified in Inclusion Criteria 4a. Notes or records from the treating oncologist are required for documentation of treatment history. Prior treatment with at least one of the following chemotherapy schedules is required to be eligible:
  - a. At least one 6 week course of continuous daily temozolomide

CONFIDENTIAL

- b. At least six 28-day cycles given in one of the following schedules:
    1. Daily for 5 days of a 28-day cycle
    2. Daily for 21 days of a 28-day cycle
    3. Daily for 14 days of a 28-day cycle
    4. Alternating 7 days on/7 days per 28-day cycle
    5. Continuous daily dosing of a 28-day cycle.
  - c. Other schedules of temozolomide may be considered after discussion with the overall Principal Investigator.
  - d. At least 3 cycles of PCV or lomustine (CCNU) chemotherapy.
7. Patients who received anti-tumor therapy after histopathologic transformation to glioblastoma must have shown unequivocal radiographic evidence of tumor progression by contrast-enhanced MRI scan (or CT scan if MRI is contraindicated).
8. Patients must have had prior CNS radiotherapy for their glioma, including standard doses for low-grade or high-grade glioma as well as non-standard dose and fractionation, including hypofractionated regimens, stereotactic radiosurgery, etc.
9. Patients can have had any number of prior therapies, including but not limited to molecularly targeted therapies and anti-angiogenic therapies, however they must have had prior chemotherapy with either temozolomide or lomustine as per Eligibility Criteria 6.
10. Karnofsky performance status (**Attachment 2**) of  $\geq 60$ .
11. Interval of at least 6 months from the completion of any prior radiotherapy and registration. If patients have not passed an interval of at least 6 months, they may still be eligible if they meet one or more of the following criteria:
  - a. New areas of tumor outside the original radiotherapy fields as determined by the investigator, or
  - b. Histologic confirmation of tumor through biopsy or resection, or
  - c. Nuclear medicine imaging, MR spectroscopy, or MR perfusion imaging consistent with true progressive disease, rather than pseudoprogression or radiation necrosis obtained within 28 days of registration AND an interval of at least 90 days between completion of radiotherapy and registration.
12. The following time periods must have elapsed prior to start of study treatment, the following time periods must have elapsed:
  - a. 5 half-lives from any investigational agent
  - b. 4 weeks from cytotoxic therapy (except 23 days for temozolomide and 6 weeks from nitrosoureas)
  - c. 6 weeks from antibodies
  - d. Prior treatment with other immune modulating agents within fewer than 4 weeks prior to the first dose of Avelumab.
    1. Examples of immune modulating agents include blockers of CTLA-4, 4-1BB (CD137), OX-40, therapeutic vaccines, or cytokine treatments.
  - e. 4 weeks (or 5 half-lives, whichever is shorter) from other anti-tumor therapies.
13. An interval of at least 2 weeks (to start of study agent) between prior surgical resection or one week for stereotactic biopsy.
14. Adequate hematologic, hepatic, and renal function defined by absolute neutrophil count  $\geq 1.5 \times 10^9/L$ , hemoglobin  $>9$  g/dL, platelet count  $\geq 100 \times 10^9/L$  (may have been transfused), aspartate aminotransferase (AST) and alanine aminotransferase (ALT)  $\leq 2.5$  x upper limit of normal (ULN), total bilirubin  $\leq 1.5$  x ULN, and estimated creatinine clearance (CrCl)  $\geq 30$  mL/min according to the Cockcroft-Gault formula or local institutional standard method.
15. Women of child-bearing potential (WOCBP) and men able to father a child must agree to use highly effective contraception while on study drug and for 30 days after the last dose of

CONFIDENTIAL

Avelumab. WOCBP must have a negative pregnancy test within 28 days of initiation of dosing. Highly effective contraceptive measures include: stable use of oral contraceptives such as combined estrogen and progestogen and progestogen only hormonal contraception or other prescription pharmaceutical contraceptives for 2 or more menstrual cycles prior to screening; intrauterine device [IUD]; intrauterine hormone-releasing system (IUS); bilateral tubal ligation; vasectomy and sexual abstinence.

- a. Contraception is not required for men with documented vasectomy.
  - b. Postmenopausal women must be amenorrheic for at least 12 months in order not to be considered of childbearing potential.
  - c. Pregnancy testing and contraception are not required for women with documented hysterectomy or tubal ligation.
16. Willing to and capable of providing written informed consent prior to any study related procedures.
  17. Ability and willingness to comply with all study requirements, including scheduled visits, treatment plans, laboratory tests, and other study-related procedures.

